Rates of sleep disturbance among SNF residents: We have conducted studies on sleep disturbance among residents of long-term care (LTC) facilities.^{1,2,5,20,22-24,55,63} Among 118 residents at four SNFs, mean nighttime percent sleep was 65.8% (SD 20.1) based on wrist actigraphy.²⁴ This is dramatically lower than the 85% typically observed among healthy older people living in the community.⁷⁰ SNF residents had marked sleep disruption, with average sleep duration of only 20.0 minutes (SD 17.8) between awakenings during the night, and extended time in bed during the day. They had little or no bright light exposure, and little evidence of a standard routine to prepare for nighttime sleep.²⁴ In another study, we observed daytime time in bed, using observations every 15 minutes for 3 days, among 230 SNF residents in eight SNFs.^{36,71} Residents were in bed for 36% and asleep for 24% of daytime observations. Daytime in-bed time was associated with more daytime sleeping ($r = .48$, $p < .001$). Residents within the same facility had a very similar timing of daytime bedrest and transfers in and out of bed; however, residents from different facilities had very different patterns despite similar subject characteristics. This suggests that facility characteristics and routines (rather than resident characteristics and needs) determined day/night bed routines.

In another study, we found that 69% of 492 residents at four SNFs met our definition of excessive daytime sleeping (i.e., asleep $>15\%$ of observations from 9am-5pm).⁵ Of these residents, 60% also had disturbed nighttime sleep (asleep $<80\%$ of time from 10pm-6am) based on wrist actigraphy. Residents spent one third of the day in their rooms, typically in bed, and were seldom outdoors or exposed to bright light (Table 1).

Variable	$\geq 15\%$ "asleep" (N=339)	<15% "asleep" (N=153)	t or χ^2 (p-value)
% of observations asleep	37.8% (18.7%)	6.4% (4.6%)	-29.09 (<.0005)**
% of observations in bed	37.4% (27.6%)	14.8% (21.1%)	-10.00 (<.0005)
% of observations in own room	47.5% (28.6%)	26.3% (24.6%)	-8.41 (<.0005)**
% of observations outdoors	0.9% (3.7%)	2.1% (6.3%)	2.09 (.038)**
Social activities, % of observations per day	13.7% (14.8%)	29.1% (20.4%)	8.40 (<.0005)**
Physical activity, % observations per day	5.3% (8.3%)	11.6% (13.7%)	5.27 (<.0005)**

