Exclusion criteria include: 1) obtunded or comatose state, 2) inability to communicate verbally, 3) inability to consent and without surrogate, and 4) non-English and non-Spanish speaking. In keeping with QI strategies, all residents will be exposed to the environmental aspects of the intervention, as these strategies represent clinically proven non-experimental behavioral strategies with no perceptible harm. Recorded (anonymous) nurse observations, actions taken and observed outcomes will include all unit residents and will be recorded using the technology system to support staff-level interventions for any resident with a sleep behavioral issue. All staff input into this system is done without resident identification.

Step C. The collection of unit-level environmental data will focus on noise levels and documentation of resident symptoms in the MDS 3.0 (described below). MDS data will be de-identified and linked through unique random numbers. Data will include the routinely collected measures (MDS 3.0) by the facility on all consented residents as well as data from scheduled evaluations by research staff of residents who have consented to participate in evaluation components that are not part of usual clinical care. We have successfully employed this type of nested design for data collection in prior research. Federally mandated MDS 3.0 data is collected by the facility for all residents at admission and quarterly thereafter. We will obtain these data covering the time period of last collection beginning just prior to the introduction of the SLUMBER intervention, and ending at the conclusion of all data collection at each study site (nursing facility unit).

Steps D, E and F will comprise the SLUMBER intervention program itself. This process will begin as soon as the sleep team is identified, and will continue in sequence. Besides a “menu” of sleep improvement procedures, we will present the **3-component SLUMBER intervention** to unit staff: **1) Improving the nighttime sleep environment; 2) Increasing patient activity levels during the day and reducing daytime behaviors that lead to sleep disturbances at night; and 3) Identifying and assisting individual residents experiencing difficulties with sleep.** We will deliver the intervention over 3 months including the provision of five mentoring sessions and data feedback, which will cover the 3-month intervention period.

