Table 3 shows the three components, outlining the workshop content (D): targeted changes within the facility; examples of strategies staff members might identify (E; from our preliminary work); and use of data for feedback and mentoring (F).

Steps G and H will follow the 3-month intervention period. Resident (actigraphy, resident-reported symptoms and observation) and unit level measures (MDS 3.0) will be collected as “post-intervention” data for analysis.

C2. Additional features of the SLUMBER intervention:

Use of Technology to enhance SLUMBER: A key innovation in the proposed study is to use technology to display real-time data, based on our positive experience with improving depression care.³ Staff recording of sleep-related problems and actions to address these problems (using simple drop-down lists) reinforces program fidelity and provides the research team with a measure of program utility. In other words, the research team will be able to know whether staff are identifying problems and implementing the environmental and therapeutic strategies of SLUMBER that they have been coached to use by the team of mentors because these strategies will be recorded using technological applications within a HIPPA compliant web-based platform (CaseWorthyTM). This platform will support staff use of behavioral strategies as well as feedback from decibel meters that are strategically placed around the unit. **Ongoing environmental monitoring with immediate staff feedback is a key advantage of this intervention.** An additional advantage of this platform is easy access to the training content that has been provided during team meetings. These will include PowerPoint presentations as well as video-recorded recommendations from mentors. During the 3-month intervention period, staff will also be able to send video, voice, or text messages to the mentors and receive responses to their questions within 24 hours. In this way, they will be better prepared to deliver the SLUMBER program and will increase their knowledge and abilities while improving the likelihood of sustainability over time. Giving staff this type of technological support is likely to further their engagement and empowerment enabling a stronger staff-delivered program.⁸²⁻⁸⁵

SLUMBER Protocol V.8/27/2018

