Decibel meters will be placed in at least 3 locations per unit, dependent upon the physical layout of the unit. These meters have Bluetooth™ capability and will upload data in real time to the web-based platform, with archived data display comparing noise levels over time and across days for each unit. We will also place decibel meters in resident rooms and provide staff with a free decibel meter smart phone app for personal use when there is concern about noise levels and they are not near the data display. In addition to a decibel meter smart phone application, we will provide staff with free light meter applications so that they can identify and record nighttime light levels and take steps to reduce light as a potential sleep-disruptive factor. Staff will utilize all technological assists on a voluntary-only basis.

Environmental scan and monitoring for sleep promotion: As in our prior work, we will link Decibel Meter data to recorded sleep at night (based on actigraphy) using decibel meters placed in the rooms of residents who consent to actigraphy recordings. While these data may not be immediately available, staff can review decibel levels as they relate to resident sleep during mentoring meetings. Using unit decibel meter data, staff behaviors and environmental problems such as a noisy door that creaks when opened or bangs when closed can be identified and corrected. The unit Sleep Champion will be armed with data to recommend actions to reduce unwanted noise. These data, which will also be presented at unit meetings, provide an opportunity for more public display and encourage staff engagement and participation.

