Recorded data and presentation for unit staff use: Recorded data and presentation is in reference to staff observations that are recorded on a web-based platform and environmental data from decibel meter output. We will provide a dropdown list of possible observations about sleep related behavior, appropriate actions to be taken for those behaviors, and observed outcomes. For example, one observation from the dropdown will be: “resident still awake [X time] after going to bed”; possible action taken: “asked if resident needs anything” or “encouraged resident to get out of bed for quiet activity until sleepy”, outcome: “resident sleeping [X time] later”. (See Appendix 4 for sample of Behavioral Monitor dropdown choices.) Recorded data will include location, time stamp for data entry, and time of observed behavior, action taken, and observed outcome, again using dropdown menus for simplicity. This tool will provide additional information on which interventions worked for which residents. These data will also be displayed as counts on a graphical interface (bar and linear graphs) for staff to review. Graphical display will include the most recent 24 hours, and any number of historical days back to one week before implementation of the intervention on the unit. Staff will be able to see trends in how strategies were used and identify additional actions to be taken.

Directed Interventions: Staff will also have the benefit of pre-intervention RA observation results, which can be loaded into the web platform as anonymous data only. These data will be presented using the same categorical dropdowns that staff can use for their observations. With permission from the residents (or proxy), we will provide pre-intervention resident reported and actigraph results (for those who consent) to enable staff to target residents with sleep difficulties.

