Unit Meetings—content and structure (Part of Step D, above): We will conduct unit team meetings for SLUMBER training, explanation of sleep improvement strategies, and use of installed technologies. We will provide Sleep Champions (typically unit nurses) with additional training as needed so that they can serve as “content experts” and reinforce sleep strategies. Members of the professional mentor group (Drs. [name], [name], [name], and [name]) will meet with each intervention unit team five times: one pre-intervention introduction and training session (in person); three intervention period meetings at the beginning each month (JM and MC by phone/videoconference, others in person) for additional sleep related education, review of strategies, shared experiences, problem sharing, and team-based solutions; and one post 3-month intervention period for follow-up and closure (in person). Drs. [name] and [name] will travel to NYC for in-person meetings. Facilitation strategies include modeling cross-discipline collaboration between mentors, identifying and nurturing team leaders and leadership skills, and facilitating contributions from all team members. Training meetings will be recorded for review by those who cannot attend and for reinforcement during and after the intervention period. Additional training on sleep promotion strategies will be stored and delivered as “on-demand” education using the web-based platform. This web-platform approach will serve as a model for a scalable program. Access to expert clinical support through an easy-to-use communication system

SLUMBER Protocol V.8/27/2018

with timely responsiveness for all unit shifts should also serve to build stronger and more engaged teams by demonstrating the importance of the team's collective work. The mentor team will address sustainability issues at the fifth and final meeting at the end of the 3-month intervention.

Intervention monitoring and follow-up includes three activities: 1) on-line recording of web-based data for ongoing assessment of intervention fidelity; 2) monthly unit-level team meetings for reviewing recorded observations and decibel data, to facilitate review and reinforcement of the sleep program implementation; and 3) web-based "office hours" for recorded staff questions and responses by the sleep experts.

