Primary Aim 4 Measures – Sleep improvement strategies will be measured as degree of reduction in nighttime noise (by decibel meters), light exposure (lux recorded on actigraph watches), and staff recorded observations/actions on the web-interface. The strategically placed decibel meters (dictated by anticipated noise areas, e.g., nurses station and unit layout and in rooms of consented residents) will measure and continuously record the frequency of noise by decibel level and time of recording with frequency counts noted at greater than 50 and 60 decibels. The WHO recommended bedroom noise for single event noise is less than 45 decibels.¹⁰¹ During the day we will determine the number of minutes residents are exposed to light >1000 lux and the proportion of observations for which residents are NOT in bed.

C5. Other Measures: Other measures will be considered potential covariates, including acute illness events and hospital days during the study, Charlson comorbidity¹⁰² index diagnoses (as recorded in MDS 3.0 during the study period), demographics, and length of SNF stay (days) from medical records. SNF administrative files will provide data on use of sedative hypnotics (FDA-approved sedative-hypnotics, over-the-counter sleep medications, “off-label” medications, and benzodiazepines) and will be measured as change in use over time.

C6. Data Analysis and Data Monitoring

Data Analyses: The outcome variables in the study can be categorized as scheduled study assessments (e.g., those measured at baseline, and post-intervention and 3 and 6 month follow-up) and routinely collected measures (MDS 3.0 variables measured on a quarterly basis, collected by the facility). Analysis strategies for each type of measure are described below. Hypothesis 1 outcomes (wrist actigraphy) are scheduled study assessments. Hypothesis 2 outcomes include both scheduled study assessments (PSQI⁸⁷ and BADS⁸⁸) and routinely collected measures (PHQ-9⁸⁹ and Pain Assessment Interview). Hypothesis 3 outcomes include both scheduled study assessments (BCAT¹⁰⁰; observed engagement in Facility Activities) and routinely collected

measures (BIMS⁶⁶; ADLs⁹⁰). *Hypothesis 4* outcomes are scheduled study assessments (Decibel meters; actigraphy-based light meters, recorded staff interventions for residents with sleep-disturbed behaviors).

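### The anonymous, voluntary staff log can support neither resident-level attribution nor an implementation rate, although the plan uses it for fidelity and as a Hypothesis 4 outcome

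*Combined protocol and SAP*

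**What the plan says.** Under Recorded data and presentation for unit staff use (C2), staff choose an observation, an action and an observed outcome from dropdown lists. The fields are location, time of entry, time of the behavior, action and outcome. The section concludes: "This tool will provide additional information on which interventions worked for which residents".

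Other sections fix what the log contains and how it is used:

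- **Identity.** B6, repeated in Step B of C1: "All staff input into this system is done without resident identification". Entries cover all residents of the unit. Step A of C1 limits technology measurements to aggregates.
- **Voluntary use.** C2: "Staff will utilize all technological assists on a voluntary-only basis". Step A says the same.
- **Implementation.** C2, Use of Technology: "the research team will be able to know whether staff are identifying problems and implementing the environmental and therapeutic strategies of SLUMBER".
- **Fidelity.** C2, Intervention monitoring and follow-up, lists first: "on-line recording of web-based data for ongoing assessment of intervention fidelity".
- **Outcome.** C4 includes in the Aim 4 measures "staff recorded observations/actions on the web-interface". C6 names recorded staff interventions among the Hypothesis 4 outcomes and classes all of these as scheduled study assessments.
- **Individual residents.** Table 3, Component 3, uses platform data gathered by staff, with decibel data, to pick out 2–3 residents per unit.

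**The concern.** The plan gives the log properties that its design removes. To say what worked for whom needs a resident code and some account of what happens when no action is taken. Neither is described. To say how fully the program was delivered needs a denominator of occasions for action, and recording that does not depend on staff choice. Neither is described for the log.

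The stakes are in interpretation. If outcomes are null, low log counts could be read as poor delivery when staff acted without logging. If counts are high and most entries end in sleep, actions could be read as effective when the residents would have fallen asleep anyway. The Hypothesis 4 test of recorded actions also has no workable model as written.

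**Working it through.** The documents give no sample size, power or rate for the log, so there is no stated figure to reproduce. The first two steps need no arithmetic.

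**1. Can an entry be tied to a resident?** The C2 field list has no resident code, and B6 and Step B exclude one. Location may hint at a room but is not described as an identifier. Repeat entries cannot be grouped by resident or linked to actigraphy or surveys. B1 expects to consent at least 50% of about 40 residents per unit, so about 20, while the log covers all residents. Entries for consented and other residents cannot be separated.

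**2. Can the log enter the planned analysis?** C6 analyses each scheduled assessment with a mixed model that has time at four levels and residents nested within units. That model needs a resident index on every record. Anonymous entries have none, so only unit-level counts can be formed.

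**3. Does sleep after an action show that the action worked?** Inputs from A4 (118 residents at four SNFs): mean nighttime percent sleep π = 65.8% (SD 20.1), and "average sleep duration of only 20.0 minutes (SD 17.8) between awakenings during the night", so mean sleep bout s = 20.0 minutes. The re-check interval X is left open in C2; I take 5 to 60 minutes (assumption). I also assume memoryless switching between sleep and wake.

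- Implied mean wake bout: w = s(1 − π)/π = 20.0 × 0.342/0.658 = 10.4 minutes.
- P(asleep X minutes later | awake now, action has no effect) = π[1 − exp(−X(1/s + 1/w))].
- At X = 15: 1/20.0 + 1/10.4 = 0.146 per minute, and 0.658 × [1 − exp(−2.19)] = 0.585.

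| Scenario | 5 min | 15 min | 30 min | 60 min |
|---|---|---|---|---|
| A4 means (w = 10.4) | 34% | 59% | 65% | 66% |
| π = 45.7% (mean − 1 SD), s = 20.0, w = 23.8 | 17% | 34% | 43% | 46% |
| π = 85.9% (mean + 1 SD), s = 20.0, w = 3.3 | 71% | 86% | 86% | 86% |
| π = 65.8%, w = 30 (s = 57.7) | 15% | 35% | 51% | 63% |
| π = 65.8%, w = 60 (s = 115.4) | 8% | 21% | 35% | 51% |

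The last two rows are assumptions and depart from the 20.0-minute sleep bout in A4. They stand for residents noticed because they have been awake for a long time. All rows assume that entries are made whatever the outcome. If staff log successes more readily, the recorded share rises.

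**The case against.** The best defense is that the log is a staff aid. C2 also calls it a measure of program utility, its graphs show counts and trends in strategy use, and C6 contains no analysis of effectiveness by strategy. Other evidence on the environment is already planned: decibel data, lux, observations of residents not in bed, and the C6 manipulation checks. For residents who give permission, Directed Interventions (C2) lets staff see individual pre-intervention results.

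Much of this stands, and it limits what may be inferred:

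- A reader might infer that the log says nothing about implementation. It does show recorded use. What it lacks is a rate, and a way to separate non-use from non-recording.
- A reader might infer that the dropdown has no entry for taking no action. Appendix 4, which holds the sample choices, is not in the text available, so this cannot be checked. What can be said is that no such comparison is described.
- A reader might infer that log outcomes will decide what enters the Program Manual. The timeline (Table 8) lists the manual only as a task.
- A reader might want to put a number on under-recording. The documents give no recording rate.

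The defense does not remove the central problem. C2, C4 and C6 give the log fidelity and outcome roles beyond that of a staff aid, and the permission route in Directed Interventions concerns pre-intervention results, not log entries.

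**Conclusion.** The point holds. The C2 sentence contradicts the anonymity statements in B6 and C1, and the log as described can show neither that an action worked nor how fully the program was delivered. The resident-level model in C6 cannot take its entries. These conclusions rest on the text alone.

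The percentages are illustrative: 34–66% at the A4 means for X of 5–60 minutes, about 17–86% over one SD either side of mean percent sleep, and lower with long wake bouts (21–51% at 15–30 minutes when w is 30–60). A reader might settle on a narrower band such as 40–65%, but that fits only an average resident re-checked after about 6 to 30 minutes. The inputs also come from a cited study whose title describes incontinent nursing home residents, who may differ from residents of the study units. The safe conclusion is that sleep after an ineffective action can be common, so raw outcome counts are not evidence of effect.

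A reader might also expect an action versus no-action contrast to rescue the claim. It would be unrandomised and selectively logged, and a fixed re-check would add night-staff work.

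The correction is worth making because it changes what can be concluded on fidelity and Hypothesis 4. It does not touch the actigraphy or symptom analyses.

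**What to change.** - **C2, Recorded data.** Delete the sentence on what worked for which residents, or restate it as unit-level counts of recorded observations, actions and outcomes that are not evidence of effectiveness.
- **Table 3, Component 3.** Reconcile the use of platform data to pick out 2–3 residents with the anonymity statements in B6 and C1, by stating which data source identifies them and under what permission.
- **C2, C4 and C6.** Call log counts recorded use of the tool. Analyse them as unit-level counts, outside the resident-level model. State that low counts will not be read as non-delivery.
- **Fidelity.** Report attendance at the five mentor sessions, which does not depend on logging. Headcounts would fit the Step A rule against collecting identifiable staff data. Show the noise, lux and research-assistant observations as supporting evidence of environmental change. They should not be the fidelity measure: they already serve as Aim 3 and Aim 4 outcomes, and using them for both would confuse non-delivery with lack of effect.

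The cost is wording in C2, C4, C6 and Table 3, plus an attendance count at each session. The downside is that the fidelity and strategy-use claims become weaker, and attendance shows exposure to the training, not what was done at the bedside.

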SLUMBER, every unit provides baseline and follow-up data. We will collect baseline data just prior to the intervention on a given unit and within 1 month after a 3-month exposure to the SLUMBER program. Facilities will encourage staff to continue to use intervention approaches after the 3-month intervention period. We will collect additional follow-up sleep and activity data with resident surveys and repeat wrist actigraph measures 3 and 6 months after the post-intervention period for all units to test for increased or continued benefit (sustainment) over time and assess for the possibility of reduced benefits over time (relapse). **From the intervention beginning and throughout the remaining study duration, real-time environmental data (noise via decibel meters) and observed sleep disturbance (by staff anonymous recording of sleep disturbances) will be available to SNF staff on a visible computer interface (described below) to facilitate continued use of SLUMBER strategies.** MDS 3.0 data collection will provide repeated measures of mood, cognitive function, and physical function for the full study duration (Figure 3). We selected a 3-month follow-up time point to strike a balance between sufficient time for intervention effects to emerge while considering the rapidly changing health status of LTC residents. Also, MDS data are collected quarterly and the intervention itself includes an initial mentoring session, three additional meetings over the next two months, and a follow-up session at the end of three months.

Supplement Design:

1. Overview: For this supplement application, we propose a 12-month intervention trial focused on dementia care SNF units using a modified comprehensive sleep improvement program, SLUMBER-RD, which is a mentored approach for unit staff. The study will be conducted in two urban SNFs with the goal of enhancing sleep quality, mood, cognitive performance, and activity engagement.

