Analysis of Scheduled Study Assessments: Mixed-effects models will be used to assess improvement in sleep outcomes due to the SLUMBER intervention. When applied to repeated measures designs, mixed-effects models accommodate incomplete data across time points (e.g., due to resident death) and can permit specification of a wide variety of residual covariance structures.¹⁰³ Each outcome will be analyzed using a two-level mixed-effects model with time as a fixed factor having four levels (baseline, post-intervention, 3-months, and 6-months), and residents nested within SNF units. We will also conduct a sensitivity analysis that takes into account nesting of units within facilities. Non-independence of residuals across time will be modeled using a variety of covariance structures (e.g., unstructured, compound symmetric, autoregressive) by selecting the covariance structure that provides the best fit (according to the Bayesian Information Criteria). We will assess the primary hypothesis concerning the intervention effect by comparing the average baseline score to the average post-intervention and 3-month scores. We will test the secondary hypothesis concerning withdrawal of the intervention by comparing the 3-month to 6-month data.

Analysis of Routinely Collected Measures: Routinely collected measures (for all consented residents on intervention units) will be analyzed using a three-level model in which time is nested within resident and residents are nested within SNF units.¹⁰⁴ A sensitivity analysis will consider a model in which a fourth level of

Level 1 (time) Outcome _{ijk} = $\pi_{0jk}+\pi_{1jk}(\text{Intv})+\pi_{2jk}(\text{IntvQtr})+e_{ijk}$	units nested within facilities is considered. The three-level model will include two key time varying predictors: Intv ,

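### Hypothesis 4 outcomes are assigned a resident-nested model that anonymous staff entries cannot enter and that has no unit-by-wave term for noise

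*Combined protocol and SAP*

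**What the plan says.** Section C6 (Data Analyses) sorts outcomes into scheduled study assessments and routinely collected measures. All three Hypothesis 4 measures go into the first class: the "outcomes are scheduled study assessments (Decibel meters; actigraphy-based light meters, recorded staff interventions for residents with sleep-disturbed behaviors".

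C6 (Analysis of Scheduled Study Assessments) then gives that class a single rule: "Each outcome will be analyzed using a two-level mixed-effects model with time as a fixed factor having four levels", "and residents nested within SNF units". The primary test is made by "comparing the average baseline score to the average post-intervention and 3-month scores". The residual covariance across time is chosen by BIC, and a sensitivity analysis adds nesting of units in facilities. No unit-by-wave random effect is stated.

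On the data themselves:

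- **Staff entries.** B6 and C1 (exclusion criteria) say "All staff input into this system is done without resident identification". C1 adds: "Recorded (anonymous) nurse observations, actions taken and observed outcomes will include all unit residents". C1 Step A makes use of the technology voluntary, with related measurements in aggregate only.
- **Timing of the staff platform.** A5 (Design) describes what staff will see: "From the intervention beginning and throughout the remaining study duration, real-time environmental data (noise via decibel meters) and observed sleep disturbance". C2 lets the display show "any number of historical days back to one week before implementation of the intervention on the unit".
- **Noise.** C2 and C4 (Primary Aim 4 Measures) put at least three meters in unit locations and further meters in the rooms of consented residents.
- **Outcome lists.** The opening list in C4 gives only noise and light for Aim 4. The Aim 4 measures paragraph in C4 and the Hypothesis 4 sentence in C6 add the staff recordings.

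**The concern.** The model needs an outcome measured on an identified, consented resident at four waves. Of the Hypothesis 4 measures, actigraph light has that form, and noise from a resident's room can be given it. The other two sources do not have it:

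- An anonymous staff entry cannot be attached to a resident, and it may concern someone who never consented. The only analysable form is a unit-level count, for which the plan has no method.
- A common-area decibel reading has one value per unit and time. It enters a resident-level model only if it is repeated across residents.

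Room meters raise a milder form of the same problem. Rooms on one unit share the same staff, shifts and events, so their noise can move together from wave to wave. A model without a unit-by-wave term treats that shared movement as independent information.

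Aim 4 is labelled a primary aim, and noise reduction is also the example C6 gives of a manipulation check for contamination between units in a facility. A falsely significant fall in noise would therefore mislead in two places.

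**Working it through.** **1. The plan's own figure.** Table 6 gives detectable effects for scheduled assessments with six units, 80% power and two-sided alpha 0.05. It can be reproduced from the generalised least squares variance of an incomplete stepped wedge. Each unit is observed at baseline, post-intervention and 3 months, with one step per unit, period fixed effects and a unit random intercept. Effects are in within-unit SD units, and detectable d = (1.96 + 0.84) × SE. The largest absolute difference over the 25 cells is 0.0095. Table 6 therefore rests on 10 to 18 residents per unit carrying separate information, with a stable unit effect and no unit-by-wave effect.

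**2. What the missing term does.** Let m be residents per unit and ρ the share of wave-to-wave variance common to all residents of a unit at a wave. Stable unit differences cancel in the baseline-versus-later contrast; the unit-by-wave part does not. The true variance of the contrast exceeds the modelled one by DE = 1 + (m − 1)ρ, so the approximate type I error is 2 × [1 − Φ(1.96/√DE)]. The documents give m (Tables 5 and 6) but no value of ρ, so ρ is an assumption and a range is shown.

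**3. Common-area value copied to each resident (ρ = 1, so DE = m).**

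| m | 1.96/√m | Formula | Simulation |
|---|---|---|---|
| 10 | 0.620 | 0.54 | 0.57–0.58 |
| 14 | 0.524 | 0.60 | 0.63–0.64 |
| 18 | 0.462 | 0.64 | 0.68 |

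The simulation exceeds the formula because the standard error is itself estimated from only six distinct contrast values.

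**4. Room meters, m = 14.**

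| Assumed ρ | DE | 1.96/√DE | Formula | Simulation |
|---|---|---|---|---|
| 0 | 1.00 | 1.960 | 0.05 | 0.05 |
| 0.05 | 1.65 | 1.526 | 0.13 | 0.12 |
| 0.10 | 2.30 | 1.292 | 0.20 | 0.20 |
| 0.20 | 3.60 | 1.033 | 0.30 | 0.32 |

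The simulations tested resident contrasts as independent given the unit. A short check that fitted the mixed model to fully copied data (150 runs, m = 14) gave 0.72, with convergence warnings, so only its direction is used.

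**5. Unit-level alternative.** A t-test on six unit changes (5 degrees of freedom) kept type I error at 0.045 to 0.055 throughout. Its detectable effect at 80% power is 1.43 SD of the unit-level change. That SD is on a different scale from Table 6, so 1.43 cannot be set directly against 0.37 to 0.75.

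**6. Staff entries.** The resident-nested test cannot be run on them. Suppose instead that they are totalled by unit, no recording exists before launch, and every unit logs something afterwards. All six changes are then positive, and the two-sided sign test gives 2 × (1/2)⁶ = 2/64 = 0.031, whatever staff did before the tool arrived.

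**The case against.** The strongest reply is that this is a drafting gap the analyst would close sensibly. Several parts of it stand:

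- The plan nowhere says that common-area readings will be copied to residents. Room meters exist, and C2 links their readings to residents' recorded sleep, so a resident-nested model can be fitted to them.
- C2 already describes staff recording as supporting fidelity and measuring program utility, and lists web recording for assessing fidelity. The opening list in C4 leaves staff entries out of the Aim 4 outcomes. For staff, Hypothesis 4 speaks of using strategies, whereas for noise and light it claims a decrease and an increase.
- The display reaches back one week, and C2 allows research-assistant observations from before the intervention to be loaded in the same categories.

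A reader might infer that the staff test is positive by construction. The documents do not support that: the test as written cannot be run, and a built-in rise requires both unit aggregation and no pre-launch recording. The text leaves staff recording in the earlier week open. The research-assistant observations would not clearly fill the gap, since C4 describes them as resident states over an 8-hour day, not staff actions at night.

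The reply does not remove the core point. C6 states a rule for each outcome, and that rule does not fit two of the data sources. BIC selection deals with correlation across time, and the facility sensitivity analysis with stable clustering. Neither captures movement shared by a unit at a particular wave.

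**Conclusion.** The concern holds in a limited form. As written, C6 assigns staff entries to a model they cannot enter, does not say which meters define noise, and omits the unit-by-wave term that noise needs. Actigraph light is measured on the resident and fits the stated nesting.

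The size depends on a choice the plan leaves open. Copied common-area values give a type I error of about 0.57 to 0.68. Room meters at 14 per unit give about 0.05 to 0.32 over assumed shares of 0 to 0.20. A reader might take the higher range as the error rate of the planned noise test. It is not: it needs copying, which the plan does not state, and all wave-to-wave variation at unit level. For room meters the inflation could be nil if ρ is zero, and nothing in the documents fixes ρ.

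For staff entries the problem is an undefined analysis, with a built-in rise only under the two conditions described. Table 6 does not describe power for unit-level noise in either case.

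**What to change.** Amend C6, with matching edits in C4:

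1. Name the noise outcome by meter location, common-area or in-room, and say how continuous records are reduced to waves.
2. Analyse common-area noise as unit-night or unit-wave summaries, with small-sample degrees of freedom based on six units.
3. For room meters, keep residents nested in units but add a unit-by-wave random effect, again with small-sample degrees of freedom.
4. Remove staff entries from the baseline-versus-later test. Report them from launch as descriptive fidelity counts per unit-week, as C2 already suggests. Reconcile the opening Aim 4 list in C4 with the Aim 4 measures paragraph and the Hypothesis 4 sentence in C6.
5. State that Table 6, built on 10 to 18 residents per unit, does not describe power for unit-level noise.

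The cost is SAP wording, with no new data collection. Intervals for noise will be wider, and one part of Hypothesis 4 becomes descriptive.
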